3.3.4.1 Discontinuation of trial treatment

An individual patient will discontinue trial treatment if:

- The patient wants to discontinue trial treatment, and or the parent(s)/legal guardian wants the patient to discontinue trial treatment, without the need to justify the decision.
- The patient has repeatedly shown to be non-compliant with important trial procedures and, in the opinion of both, the investigator and sponsor representative, is not willing or able to adhere to the trial requirements in the future.

In the following cases discontinuation of trial medication is highly recommended. Only in special circumstances the investigator, upon thorough assessment of all available clinical data and taking into consideration the potential risks associated with administration of nintedanib, may decide not to withdraw the trial medication, even though one or more of the below mentioned criteria are fulfilled. In such a case, continuation of treatment with trial medication should be discussed with the patient's parent(s)/legal guardian, and the decision and reasoning documented in the source data.

- Major surgery, including any abdominal or intestinal surgery.
- Anti-coagulation. Patients who require full-dose therapeutic anticoagulation (e.g. vitamin K antagonists, heparin, hirudin, direct thrombin inhibitors, etc.), or high-dose antiplatelet therapy. Prophylactic low dose heparin or heparin flush as needed for maintenance of an indwelling intravenous device (e.g. enoxaparin 4000 I.U. s.c. per day), as well as prophylactic use of antiplatelet therapy (e.g. acetyl salicylic acid up to 325 mg/day, or clopidogrel at 75 mg/day, or equivalent doses of other antiplatelet therapy) is allowed.
- Major thrombo-embolic events e.g. stroke, deep vein thrombosis, pulmonary embolism, myocardial infarction.
- Increased risk of bleeding e.g. haemorrhagic CNS event, gross / frank haemoptysis or haematuria, active gastro-intestinal bleeding or GI-ulcers.

The trial medication has to be permanently discontinued in the following circumstances:

- The patient experiences signs of hepatic injury, as defined in [Section 5.2.7.1.4](#).
- In the opinion of the Investigator, the patient experiences unacceptable adverse events despite dose adjustments and supportive care, as defined in [Section 4.1.2](#).
- The patient needs to take concomitant medication that is restricted as defined in [Section 4.2.2](#).
- The patient can no longer receive trial treatment for medical reasons (such as adverse events, other diseases, or pregnancy).

If a patient becomes pregnant during the trial the investigational product must be discontinued immediately, and the patient will be followed up until birth or otherwise termination of the pregnancy. The data of the patient will be collected and reported in the clinical trial report (CTR) until patient's last visit, and any events thereafter will be reported in the Boehringer Ingelheim (BI) drug safety database. Refer to [Section 5.2.7.2.3](#) for detailed information on event reporting in case of pregnancy.

In case of discontinuation of trial medication, it is of utmost importance for the robustness and integrity of the trial results that the patient remains in the study and returns to all

regularly scheduled visits until the end of the trial. For those patients who are unable to complete the scheduled visits, every attempt will be made to get information on vital status at 24 weeks after randomization, i.e. the time of the data cut-off for the primary analysis, at 52 weeks after randomization and at the end of the trial, as outlined in the [Flow Chart](#) and [Section 6.2.3](#).

3.3.4.2 Withdrawal of consent to trial participation

Patient's parent(s)/legal guardian may withdraw their consent to trial participation (and/or the patient may withdraw assent, where applicable) at any time without the need to justify the decision.

If a patient's parent(s)/legal guardian wants to withdraw consent (and/or the patient wants to withdraw assent, where applicable), the investigator should be involved in the discussion with the parent(s)/legal guardian (and/or the patient) and explain the difference between trial treatment discontinuation and withdrawal of consent to trial participation, as well as explain the options for continued follow-up after trial treatment discontinuation, please see [Section 3.3.4.1](#) above.

3.3.4.3 Discontinuation of the trial by the sponsor

Boehringer Ingelheim reserves the right to discontinue the trial overall or at a particular trial site at any time for the following reasons:

1. Failure to meet expected enrolment goals overall or at a particular trial site.
2. Emergence of any efficacy/safety information invalidating the earlier positive benefit-risk-assessment that could significantly affect the continuation of the trial.
3. Deviations from GCP, the trial protocol, or the contract impairing the appropriate conduct of the trial.

The investigator / the trial site will be reimbursed for reasonable expenses incurred in case of trial termination (except in case of the third reason).

4. TREATMENTS

4.1 INVESTIGATIONAL TREATMENTS

The investigational medicinal products are nintedanib soft capsules 150 mg, 100 mg, 25 mg, and matching placebo capsules.

Nintedanib soft capsules 100 mg (oblong shape, 6.2 mm diameter and 16.3 mm length) and 150 mg (oblong shape, 7.1 mm diameter and 17.6 mm length) are commercially available for adults. Nintedanib soft capsules 25 mg of smaller size (oval shape, 5.1 mm diameter and 8.0 mm length) have been developed for this trial in the paediatric population. The 75 mg and 50 mg doses will be provided as multiples of the newly developed 25 mg dosage strength.

The sizes of the commercially available 100 mg and 150 mg capsules are considered suitable for the targeted age-range. However, for patients who are unable to swallow the commercially available form, a multiple of the 25 mg capsule is proposed as an alternative administration strategy for the 100 mg or 150 mg:

- 4 x 25 mg for the 100 mg
- 6 x 25 mg for the 150 mg

4.1.1 Identity of the Investigational Medicinal Products

Table 4.1.1:1 Test product 1

| | |
|-----------------------------|--|
| Substance: | Nintedanib (Ofev [®]) |
| Pharmaceutical formulation: | Soft gelatin capsule |
| Source: | Boehringer Ingelheim Pharma GmbH & Co. KG |
| Unit strength: | 150 mg, 100 mg, 25 mg |
| Posology: | 150 mg, or 100 mg, or 3x25 mg, or 2x25 mg, or 25 mg, each b.i.d. |
| Mode of administration: | Oral (swallowed) |

Table 4.1.1:2 Test product 2

| | |
|-----------------------------|---|
| Substance: | Placebo |
| Pharmaceutical formulation: | Soft gelatin capsule |
| Source: | Boehringer Ingelheim Pharma GmbH & Co. KG |
| Unit strength: | Placebo to 150 mg, 100 mg, 25 mg |
| Posology: | Placebo to 150 mg, or 100 mg, or 3x25 mg, or 2x25 mg, or 25 mg, each b.i.d. |
| Mode of administration: | Oral (swallowed) |

4.1.2 Selection of doses in the trial and dose modifications

In order to match the systemic exposure reached in adult IPF patients, the nintedanib doses in paediatric patients were predicted based on body weight dependent allometric scaling (scaling of adult clearance using an exponent of 0.75, consistent with the exponent estimated in population pharmacokinetics [PopPK] analyses in adults; refer to the current version of the Investigator's Brochure Nintedanib in Idiopathic Pulmonary Fibrosis, Systemic Sclerosis and Progressive Fibrosing Interstitial Lung Disease [[c01783972-16](#)] for details). This approach is considered acceptable, assuming a minor role of developmental changes referring to nintedanib PK for the selected target population. A population mean nintedanib exposure of 80% to 125% compared to adult IPF patients treated with 150 mg b.i.d. was targeted for the determination of the planned doses by body weight bin in the paediatric population as provided in [Table 4.1.2: 1](#).

The patient's weight will be measured at screening, at randomization and at each IMP dispensing visit thereafter (see [Flow Chart](#) for details). At randomization the dose assigned will be based on the patient's weight at baseline (Visit 2). At subsequent visits the dose will be adjusted for any changes of the patient's weight resulting in a change of the body weight bin. IRT will assign the proper dose based on the patient's weight recorded at the respective visit.

Table 4.1.2: 1 Dose assignment and dose reduction possibilities based on body weight bins according to ICH E11

| Body weight bin | Weight range | Dose (b.i.d.) | Capsule strengths | Dose reduction possibility (b.i.d.) | Capsule strengths |
|-----------------|-------------------|---------------|---------------------------|-------------------------------------|---------------------------|
| 1 | 13.5* to <23.0 kg | 50 mg | 25 mg (2x) | 25 mg | 25 mg (1x) |
| 2 | 23.0 to <33.5 kg | 75 mg | 25 mg (3x) | 50 mg | 25 mg (2x) |
| 3 | 33.5 to <57.5 kg | 100 mg | 100 mg (1x) or 25 mg (4x) | 75 mg | 25 mg (3x) |
| 4 | ≥57.5 kg | 150 mg | 150 mg (1x) or 25 mg (6x) | 100 mg | 100 mg (1x) or 25 mg (4x) |

* Patients <13.5 kg of weight are excluded from the trial

Based on population anthropometric measures of weight by age, most children younger than 10 are expected to fall into body weight bin 1–2, younger adolescents in bin 3 and older ones in bin 4.

Similar to the adult dosing schedule [[P17-10582](#)], treatment interruption and dose reduction are allowed as medically indicated.

Criteria for dose reduction / treatment interruption

Treatment should be interrupted in case the patient experiences a weight decrease below 13.5 kg. Treatment can be resumed when patient's weight reaches the threshold of 13.5 kg.

If a patient experiences a drug related adverse event, the dose can be reduced to the next lower dose and the dose can be re-started after recovery. The dose reduction scheme in [Table 4.1.2: 1](#) should be considered to manage adverse events.

The dose can be reduced without prior interruption, i.e. immediately stepping down from one dose to the next dose.

If the reduced dose is well tolerated, re-escalation is possible within 4 weeks after dose reduction in case of AEs considered drug related, or within 8 weeks in case of AEs not considered drug related. If this occurs between scheduled visits, this will also require an unscheduled visit.

Dose reduction and re-increase are allowed at multiple occasions.

No further dose reduction outside of those listed will be allowed. In case of persistent adverse events observed at the reduced dose, or severe effects at the starting dose, permanent treatment discontinuation should be considered.

Temporary treatment interruption is allowed to manage adverse events (see below for details).

In case of pathological findings identified on follow-up bone imaging, or stunted growth identified on follow-up dental imaging, treatment should be interrupted, the patient case presented to the SMC by the sponsor and recommendations for next steps obtained. Treatment may be resumed upon recommendation of the SMC.

The criteria to be followed for treatment interruption, re-start and re-escalation are shown in [Table 4.1.2: 2](#).

Table 4.1.2: 2 Allowed treatment reduction / interruption periods:

| | AEs considered related to study drug | AEs or other events not considered related to study drug |
|---|---|---|
| Maximum interruption | 4 weeks | 8 weeks |
| Recommended restart of treatment | with reduced dose per Table 4.1.2: 1 | with the same dose as before interruption |
| Re-escalation | re-escalation to the dose assigned per Table 4.1.2: 1 may occur any time per investigator judgement | n.a. |

To manage diarrhoea and liver enzyme elevations guidelines similar to the adult programme are provided in the paediatric programme.

- Management of diarrhoea

Diarrhoea is a known and the most frequent side effect of nintedanib treatment. However, potential causes for diarrhoea other than trial medication should always be considered and treated accordingly (e.g. viral infections, bacterial overgrowth, and antibiotic treatment). Diarrhoea should be managed as early as possible after onset of first symptoms with standard antidiarrheal symptomatic treatment, e.g. loperamide.

If diarrhoea persists despite optimal symptomatic treatment, treatment interruption and/or dose reduction of nintedanib should be considered. [Table 4.1.2: 3](#) shows the recommendations for children and adolescents with the appropriate age and weight-adjusted dosing.

Table 4.1.2: 3 Management of diarrhoea (considered related to trial medication) in children and adolescents

| Description | Symptomatic Treatment* | Action with trial medication |
|---|---|---|
| Diarrhoea with increase of <4 stools per day over baseline¹ | Initiate anti-diarrhoeal medicines at first signs of symptoms e.g. loperamide, as per the age-adjusted dosing regimen (Table 4.1.2:4) until bowel movements cease for 12 hours. Monitor for signs or symptoms of dehydration. Consider oral rehydration therapy. | Continue same trial medication dose. |
| Diarrhoea with increase of 4 to 6 stools per day over baseline¹ | Initiate/continue anti-diarrhoeal medicines; If diarrhoea of this severity persists for ≥48 to 72 hours assess for dehydration and electrolyte imbalance; In addition, consider i.v. fluids and electrolyte replacement as clinically indicated. | If diarrhoea persists for ≥48 to 72 hours despite optimal symptomatic care: 1. Interrupt trial medication until recovery. 2. Reduce dose to the next lower dose after recovery. 3. Re-escalate to the weight-adjusted dose within 4 weeks if deemed clinically appropriate. |
| Diarrhoea with increase of ≥7 stools per day over baseline¹; stool incontinence, or life threatening consequences | Follow recommendations above. In addition, consider stool work-up to exclude infectious colitis; adequate i.v. fluid replacement ≥24 hours, hospitalization as clinically indicated; consider referral to a GI specialist to rule out potential differential diagnoses. | 1. Interrupt trial medication until recovery. 2. Reduce dose to the next lower dose after recovery. 3. Consider re-escalation within 4 weeks to the weight-adjusted dose if deemed clinically appropriate. In case of reoccurrence of diarrhoea of this severity despite optimal symptomatic treatment and dose reduction, treatment with trial medication should be permanently discontinued. |

Footnotes:

* Other potential causes for diarrhoea should always be considered and treated accordingly (e.g. viral infections, bacterial overgrowth, antibiotic treatment)

¹ Baseline defined as usual stools/day prior randomization.

Table 4.1.2: 4 Loperamide dose regimen based on group age

| Group age | Posology |
|----------------------|---|
| Children 6-8 years | One 5 ml (1 mg) dose three or four times daily with the duration limited to 3 days |
| Children 9-11 years | Two 5 ml (1 mg) doses four times daily with the duration limited to 5 days |
| Children 12-17 years | 4 mg followed by 2 mg after each loose stool or every 2-4 hours to a maximum of 12 mg/day |

- Management of liver enzyme elevations

Nintedanib can be associated with increased liver enzymes. Concomitant use of other drugs known to cause liver enzyme elevations should be evaluated. For a detailed guidance on how to manage liver enzyme elevations, please refer to [Table 4.1.2: 5](#).

Table 4.1.2: 5 Recommendations for managing liver enzyme elevations

| | AST or ALT increase to | | | Signs of hepatic injury* |
|-----------------------------------|--|--|--|---|
| | >1.5x to <3x ULN | ≥3x to <5x ULN and no signs of hepatic injury | ≥5x to <8x ULN and no signs of hepatic injury | |
| Visit 2 (randomization) | Permanently discontinue trial medication or justify continuation ¹ | Permanently discontinue trial medication | Permanently discontinue trial medication | Permanently discontinue trial medication |
| Any other Visit | Continue as planned ² | Reduce dose or interrupt trial medication ³ | Interrupt trial medication | Permanently discontinue trial medication |
| | | Close observation ⁴ After 2 weeks or any time later | Close observation ⁴ After 2 weeks or any time later | CLINICAL EVALUATION OF HEPATIC-INJURY⁵ |
| | | | | |
| | <3x ULN | ≥3x ULN | <3x ULN | ≥3x ULN |
| | Reduced: return to initial dose. Interrupted: restart at reduced dose. Monitor every 2 weeks for at least 8 weeks | Permanently discontinue trial medication Close observation ⁴ | Restart at reduced dose Monitor weekly for 4 weeks, then every 2 weeks for at least 8 weeks | Permanently discontinue trial medication. Close observation ⁴ |

Footnotes:

*Signs of hepatic injury are defined as

- ALT and/or AST ≥8 fold ULN
- ALT and/or AST ≥3 fold ULN and total bilirubin ≥2 fold ULN
- ALT and/or AST ≥3 fold ULN and unexplained INR >1.5
- ALT and/or AST ≥3 fold ULN and unexplained eosinophilia (>5%)
- ALT and/or AST ≥3 fold ULN and appearance of fatigue, nausea, vomiting, right upper abdominal quadrant pain or tenderness, fever and/or rash

¹Investigator to confirm in writing that continuation is justified (e.g. intermittent fluctuation of transaminases).

²According to visit schedule. Consider additional control visits as adequate.

³To be decided by Investigator, based on individual risk assessment.

⁴Close observation: Re-test ALT and AST, alkaline phosphatase, total bilirubin, and eosinophils within 48 to 72 hours, then approximately 7 days, then approximately 2 weeks by using intermediate visit lab kit.

Initial assessment of liver enzyme elevation should be performed at the investigational site. Blood samples for additional monitoring may be collected at the investigational site, primary care physician or external laboratory with specific trial lab kits and sent to the central laboratory for analysis.

- Management of acute ILD exacerbations

In case of acute ILD exacerbations or clinical deterioration, all treatment options considered adequate by the Investigator are allowed. The patient may interrupt study treatment for up to 8 weeks, if necessary (e.g. if short-term full anticoagulation is performed).

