As the most common side effects known for nintedanib are GI effects i.e. diarrhoea, nausea and vomiting (see [Section 1.4.2](#)) the concomitant use of medication with an overlapping safety profile (e.g. mycophenolate mofetil) should be carefully considered.

Nintedanib is also associated with increases in liver enzymes and bilirubin. If in addition to the trial medication, a treatment is introduced that is known to induce AST/ALT elevations (e.g. methotrexate, bosentan), additional measurements of liver enzymes (ALT and AST, alkaline phosphatase, total bilirubin, and eosinophils) every 2 weeks for approximately 6 weeks, by using intermediate (a-visit) trial lab kit are recommended.

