5.2.3 Safety laboratory parameters

Safety laboratory parameters to be assessed are listed in [Table 5.2.3: 1](#). For the sampling time points please see the [Flow Chart](#).

All analyses will be performed by a central laboratory, the respective reference ranges will be provided in the ISF.

Patients do not have to be fasted for the blood sampling for the safety laboratory.

Instructions regarding sample collection, sample handling/ processing and sample shipping are provided in the Laboratory Manual in the ISF.

The central laboratory will send reports to the investigator. It is the responsibility of the investigator to evaluate the laboratory reports. Clinically relevant abnormal findings as judged by the investigator will be reported as adverse events (please refer to [Section 5.2.7.1.1](#)).

In case the criteria for hepatic injury are fulfilled, a number of additional measures will be performed (please see [Section 5.2.7.1.4](#) and the DILI Checklist provided in the electronic Data Capture (eDC) system. The amount of blood taken from the patient concerned will be increased due to this additional sampling.

The central laboratory will transfer the results of the analysis to the sponsor.

Table 5.2.3: 1 Safety laboratory tests at regular site visits

The laboratory tests at regular site visits will include:

| Category | Laboratory test |
|--------------|---|
| Haematology | Red blood cell count (RBC) Haemoglobin (Hb) Haematocrit (Hct) Mean corpuscular volume White blood cell count including differential count Platelet count |
| Biochemistry | Aspartate aminotransferase (AST) Alanine transaminase (ALT) Gamma-glutamyl transferase (GGT) Alkaline phosphatase (ALK) Creatine kinase (CK) Lactate dehydrogenase (LDH) Total protein Total bilirubin Creatinine Glucose (non fasting, V1 and V2 only) Uric acid Thyroid stimulating hormone β-HCG (at all visits requiring blood sampling for laboratory tests until EoT– in all and only female patients)* |
| Electrolytes | Sodium Potassium Calcium Chloride Inorganic phosphorus |
| Coagulation | International normalized ratio (INR) Activated partial thromboplastin time (aPTT) Prothrombin time (PT) |
| Urinalysis | pH, glucose, erythrocytes, leukocytes, protein, nitrite (semi-quantitative measurements; -, +, ++, +++) |

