*Pregnancy test is required in all female patients every 4-6 weeks, either at home or at site. β-HCG test on blood will be conducted at all visits until end of treatment on blood collected for laboratory tests. Locally provided urine dipstick pregnancy tests will be dispensed for use between clinic visits starting from Visit 4. A urine dipstick pregnancy test will be conducted at the Follow-up Visit (if acceptable) and test results will be documented in the patient's records. In case of positive results, procedures defined in [Section 5.2.7.2.3](#) should be followed.

Table 5.2.3:2 Safety laboratory tests at intermediate ‘a’-visits

The laboratory tests at intermediate ‘a’-visits will include:

| Category | Laboratory test |
|--------------|---|
| Biochemistry | Total protein, creatinine, electrolytes and liver function (AST, ALT, GGT, alkaline phosphatase, and total bilirubin) |
| Urinalysis | pH, glucose, erythrocytes, leukocytes, protein, nitrite (semi-quantitative measurements; -, +, ++, +++) |

At ‘a-Visits’, safety blood, and urine samples will be collected and submitted to the central laboratory if needed for additional safety monitoring at the discretion of the Investigator (see cautionary notes under [Section 4.2.2.1](#) for additional safety monitoring).

The samples may be collected at the office of a local doctor using trial specific lab kits that will be sent to a central laboratory for analyses. These kits will be provided to patients at study visits as applicable.

A maximum total amount of approximately 38 mL blood will be taken for standard safety laboratory tests during the course of Part A. In Part B, a maximum total amount of approximately 44 mL blood will be taken for standard laboratory (this is based on a 76-week duration of Part B, but it might be less depending of the time the patient will stay in Part B).

Creatinine clearance will be calculated based on serum creatinine according to Schwartz formula [[R10-0828](#), [R11-4789](#)] (see [Appendix 10.2](#)).

If laboratory values indicate abnormality, adequate and more frequent blood sampling may be performed at the discretion of the Investigator.

In case of liver function value elevations, close monitoring must be ensured by the Investigator. Refer to [Section 4.1.2](#) for monitoring elevations and [Section 3.3.4](#) for withdrawal criteria.

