5.2.7.1.4 Adverse events of special interest

The term adverse events of special interest (AESI) relates to any specific AE that has been identified at the project level as being of particular concern for prospective safety monitoring and safety assessment within this trial, e.g. the potential for AEs based on knowledge from other compounds in the same class. AESIs need to be reported to the sponsor’s Pharmacovigilance Department within the same timeframe that applies to SAEs, please see [Section 5.2.7.2.2](#).

The following are considered as AESIs:

- adverse events relating to gastrointestinal perforation
- bleeding
- hepatic injury
- pathological findings identified on bone imaging
- stunted growth identified on dental imaging

Hepatic injury

In this trial protocol, signs of hepatic injury are defined as:

- ALT and/or AST ≥ 8 fold ULN
- ALT and/or AST ≥ 3 fold ULN and total bilirubin ≥ 2 fold ULN*
- ALT and/or AST ≥ 3 fold ULN and unexplained INR $> 1.5^*$
- ALT and/or AST ≥ 3 fold ULN and unexplained eosinophilia ($>5\%$)*
- ALT and/or AST ≥ 3 fold ULN and appearance of fatigue, nausea, vomiting, right upper abdominal quadrant pain or tenderness, fever and/or rash

*in the same blood draw sample.

These lab findings constitute a hepatic injury alert and the patients showing these lab abnormalities need to immediately stop the trial medication and be followed up according to the “DILI checklist” provided in the eDC system. The investigator is asked to collect requested information within 48 hours upon laboratory hepatic injury alert/notification.

In case of clinical symptoms of hepatic injury (icterus, unexplained encephalopathy, unexplained coagulopathy, right upper quadrant abdominal pain, etc.) without lab results (ALT, AST, total bilirubin) available, the investigator should make sure these parameters are analysed, if necessary in an unscheduled blood test. Should the results meet the criteria of hepatic injury alert, the procedures described in the DILI checklist should be followed.

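### The a-visit laboratory panel has no eosinophils and no INR, so two of the five hepatic-injury stopping criteria cannot be judged on close-observation re-tests

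*Protocol*

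**What the plan says.** Protocol 4.1.2, Table 4.1.2: 5, sets the action for raised ALT or AST. Its two middle columns (3x to <5x ULN and 5x to <8x ULN) apply only if there are no signs of hepatic injury. They lead to close observation, which footnote 4 defines: "Re-test ALT and AST, alkaline phosphatase, total bilirubin, and eosinophils within 48 to 72 hours", then at about 7 days, then at "approximately 2 weeks by using intermediate visit lab kit".

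Section 4.2.2.1 recommends the same five tests from the same kit when a drug known to raise transaminases is introduced: "additional measurements of liver enzymes (ALT and AST, alkaline phosphatase, total bilirubin, and eosinophils) every 2 weeks".

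Table 5.2.3:2 gives the blood tests at a-visits as "Total protein, creatinine, electrolytes and liver function (AST, ALT, GGT, alkaline phosphatase, and total bilirubin"), with urinalysis in addition. SAP Table 7.8.2.1: 2 repeats this list. The regular-visit panel (Table 5.2.3: 1) does have the two other tests: "White blood cell count including differential count Platelet count" under haematology and "International normalized ratio (INR) Activated partial thromboplastin time (aPTT") under coagulation.

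Section 5.2.7.1.4 lists five signs of hepatic injury. Three of them (with bilirubin, INR or eosinophilia) must be met "in the same blood draw sample" as the transaminase elevation. On a positive finding, "the patients showing these lab abnormalities need to immediately stop the trial medication", and section 3.3.4.1 makes that discontinuation permanent.

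**The concern.** The protocol asks for a test from a kit whose listed contents do not include it. The choice of action depends on the answer. To place a child in either middle column of Table 4.1.2: 5, the site must know that none of the five signs is present. On a sample limited to the a-visit panel, two of them are unmeasured.

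If ALT/AST then falls below 3x ULN at two weeks or later, the table returns a dose-reduced child to the initial dose and restarts an interrupted child on a reduced dose. If an earlier a-visit draw would have shown eosinophilia or a raised INR alongside ALT/AST of 3x ULN or more, that child should have stopped permanently. In the dose-reduction branch the child also stays on drug throughout close observation. The protocol's risk table (1.4.2) describes drug-induced liver injury as potentially fatal and names the a-visit kits as part of the mitigation for enzyme elevations.

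There is a smaller analysis consequence. SAP 5.4.4 summarises the same five criteria and SAP 7.8.2.2 plots eosinophils in the liver profiles. A-visit draws on the listed panel would supply neither eosinophils nor INR.

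**Working it through.** The plan gives no figure to reproduce. The check sets the test lists side by side.

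| Test | Footnote 4 | 4.2.2.1 | A-visit panel (Table 5.2.3:2; SAP Table 7.8.2.1: 2) | Regular panel (Table 5.2.3: 1) |
|---|---|---|---|---|
| ALT, AST | yes | yes | yes | yes |
| Alkaline phosphatase | yes | yes | yes | yes |
| Total bilirubin | yes | yes | yes | yes |
| Eosinophils (differential) | yes | yes | **no** | yes |
| INR | **no** | **no** | **no** | yes |

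**Tests asked for against tests on the kit.** Footnote 4 names 5 tests (ALT, AST, alkaline phosphatase, total bilirubin, eosinophils). The panel has 5 − 1 = 4 of them.

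**Criteria that can be judged on the panel.** Of the 5 signs in 5.2.7.1.4:

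1. ALT/AST at 8x ULN or more: yes.
2. ALT/AST at 3x ULN or more with bilirubin at 2x ULN or more: yes.
3. ALT/AST at 3x ULN or more with unexplained INR above 1.5: no.
4. ALT/AST at 3x ULN or more with unexplained eosinophilia above 5%: no.
5. ALT/AST at 3x ULN or more with the listed symptoms: yes.

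So 2 cannot be judged and 5 − 2 = 3 can. The same-draw rule also means that a later INR or eosinophil count, taken without ALT/AST, does not fill the gap.

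**Where the missing tests could change the action.** Close observation has 3 re-tests (48–72 hours, about 7 days, about 2 weeks). At two weeks, ALT/AST of 3x ULN or more is already a permanent stop, and below 3x ULN neither criterion can be met. That leaves 3 − 1 = 2 re-tests, plus the first draw if it was itself an a-visit.

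**Which branches are exposed.** A dose reduction between visits brings an unscheduled site visit with safety laboratory tests (4.1.4 and 6.2.2). Taking these as the regular panel, both tests are then available at that visit. An interruption has no such visit: 4.1.4 only refers back to 4.1.2, and interruption is the only action at 5x to <8x ULN. For an interrupted child the dose-change visit comes at restart, when ALT/AST is already below 3x ULN. The gap is therefore mainly the interruption-only branch and the close-observation re-tests themselves.

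**A related wording difference.** The footnote to Table 4.1.2: 5 repeats the five signs without the same-draw condition that 5.2.7.1.4 and SAP 5.4.4 attach to three of them. Section 5.2.7.1.4 governs, because 3.3.4.1 cites it, but the table alone could be read as allowing values from different draws.

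**The case against.** The eosinophil mismatch is plain on the page. The best counter-case concerns INR and the size of the harm.

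- **INR is not requested on this kit.** Footnote 4 and the panel agree in omitting it, so on INR there is no contradiction between the two. That is true. But INR is one of the plan's own same-draw stopping criteria, so a re-test used to manage a child as free of hepatic injury needs it.
- **Other steps catch the case.** Initial assessment should take place at the site, regular visits carry both tests, and extra sampling is allowed at the investigator's discretion. These help at the first draw. None adds either test to the later re-tests, which may be drawn elsewhere, and the text visible to us does not name the tests at the initial assessment. The DILI checklist starts only after a hepatic-injury alert, so it cannot detect a criterion that was not measured.
- **The drug is already reduced or interrupted.** This stands and narrows the harm to two situations: continued exposure on a reduced dose, and return to drug after a criterion was met only on an a-visit draw.
- **The missing same-draw condition errs on the cautious side.** It could only stop more children. That stands, and the point is secondary.
- **The documents are incomplete.** The text of footnote 5 to the table is not visible in our copy, and the Laboratory Manual is not available. We therefore do not claim that a cross-reference is absent or that the physical kit lacks these tests.
- **Table 4.1.2: 5 and section 4.2.2.1 are recommendations.** That is so, although footnote 4 is worded as an instruction and the permanent stop is mandatory.

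**Conclusion.** The concern holds. The a-visit panel lists 4 of the 5 tests in footnote 4, and 2 of the 5 hepatic-injury criteria cannot be judged on it. The missing results could change the action at 2 of the 3 close-observation re-tests, and at the first draw if that was an a-visit. Few children would be affected; the documents give no rate of transaminase elevation in this population, so no count is estimated. The primary PK and adverse-event analyses, the AESI definition and the SAP definition of hepatic injury are not affected.

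This rests on the a-visit kit measuring what Table 5.2.3:2 lists. If the Laboratory Manual shows that the kit already measures eosinophils, the table and its SAP copy are still wrong, and INR still has to be added to footnote 4. The change should be made because it lets an existing safety rule be applied as written.

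**What to change.** - **Protocol Table 5.2.3:2:** add the white-cell differential (eosinophils) and INR to the a-visit panel for liver re-tests. Use the same panel for the monitoring draws in 4.2.2.1, which already name eosinophils.
- **Protocol Table 4.1.2: 5, footnote 4:** add INR.
- **Protocol Table 4.1.2: 5, list of hepatic-injury signs:** add the same-sample asterisk, or a cross-reference to 5.2.7.1.4, to the bilirubin, INR and eosinophilia items.
- **SAP Table 7.8.2.1: 2:** update to match.
- **Central laboratory:** confirm the kit contents.

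Protocol 5.2.7.1.4 and 3.3.4.1 and SAP 5.4.4 need no change.

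Beyond the edits, the cost is a slightly larger blood volume at these draws. The protocol gives only maximum totals for standard safety tests (about 38 mL in Part A and 44 mL in Part B), not a volume per kit, so the increase cannot be quantified from the documents.
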